155 orals agents [40, 41, 43-48]. It is still not known whether these favorable effects extent to  
156 the more challenging group of patients with type 2 diabetes who have a baseline HbA1c  
157 >10%. Liraglutide reduces blood glucose by several mechanisms independent of insulin  
158 secretion and its superior effect on HbA1c and weight loss was found to be largely  
159 independent of diabetes duration and baseline HbA1c [39]. Treatment with GLP-1  
160 agonists has also been associated with low secondary failure rates, durable and sustained  
161 long term blood glucose control, and durability of the initial weight loss [39, 42, 49].

162

163 **Given all these distinct properties of GLP-1 agonists and simplicity of use, we**  
164 **propose they could represent a viable alternative to intensive insulinization in**  
165 **patients with very uncontrolled (HbA1c >10%) type 2 diabetes.**

166

167 The aim of this study is to compare a GLP-1 plus basal insulin treatment regimen to a  
168 basal-bolus treatment regimen in patients with very uncontrolled (HbA1c>10%) type 2  
169 diabetes. We will compare the two regimens with respect to efficacy in improving  
170 glycemic control, rate of hypoglycemia, change in weight, effect on patient quality of  
171 life, treatment burden, physician time, as well as healthcare related cost. We hypothesize  
172 that the two treatment regimens will have equal effectiveness, while the GLP-1 based  
173 regimen will be superior with respect to all other variables.

174

175 We chose to focus on a specific patient population which is generally considered to be  
176 most challenging to manage, use up greater healthcare resources, have higher potential for  
177 morbidity, and have traditionally been excluded from most clinical trials. Therefore this  
178 study will fill in an existing knowledge gap and provide high level evidence for future  
179 diabetes treatment guidelines pertaining to this patient population. We will obtain  
180 information not only in regards to the effectiveness of the treatment, but also safety and  
181 impact on healthcare cost beyond the cost of the drug.

182

183 Our findings will have great impact on the way we treat this – unfortunately – significant  
184 segment of the diabetic population, with huge potential benefits beyond just glycemic  
185 control, including quality of life, other metabolic co-morbidities, healthcare cost, etc.  

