## 211 **Specific aims:**

- 212 1. Compare the two treatment regimens with respect to a disease and patient-  
213 relevant composite outcome of effectiveness (HbA1c <7%) and safety (no  
214 hypoglycemia and no weight gain);
- 215 2. Compare the two treatment regimens with respect to treatment burden (number of  
216 daily shots, amount of glucose self-monitoring, need for treatment titration);
- 217 3. Compare the two treatment regimens with respect to quality of life [as measured  
218 by a disease specific (DQOL) questionnaire and general health (SF-36)  
219 questionnaire];

220 4. Compare the two treatment regimens with respect to all healthcare related costs:  
221 actual cost of the pharmacologic agents, glucose monitoring supplies, all other  
222 pharmacologic (non-study related) and non-pharmacologic healthcare related  
223 costs (outpatient and inpatient, diabetes related and non-diabetes related). We will  
224 also compare actual physician time spent during office visits and non-visit related  
225 care of these patients. While no actual dollar amount can be attached to this  
226 (phone visits and longer office visits required by the need for extra patient  
227 education are not customarily reimbursable) time commitment is of great  
228 relevance to our physicians who care for these very complex patients.  
229

230 **Primary outcome:**

231 Change in HbA1c from randomization to 26 weeks of therapy.  
232

233 **Secondary outcomes:**

- 234 1. The main secondary outcome is a less traditional but very patient-centric and  
235 clinically meaningful composite outcome of HbA1c <7% AND no documented  
236 hypoglycemia (capillary glucose level <56 mg/dl) AND no significant weight  
237 gain (<3% body weight) during the 6-mo study follow-up;
- 238 2. % reaching target HbA1c of <7% at end of study;
- 239 3. 7-point glucose profile results;
- 240 4. % patients reaching pre-specified “treatment failure” outcome;
- 241 5. Change in weight from baseline (both absolute weight lost and percent of body  
242 weight);
- 243 6. % patients with weight loss >5% of body weight;
- 244 7. Number of hypoglycemic episodes defined as mild (symptoms of hypoglycemia  
245 confirmed by a CBG reading of <70 mg/dl), moderate (any CBG reading <56  
246 mg/dl), severe (need for help to recover regardless of CBG reading);
- 247 8. Number of patients experiencing any hypoglycemic episodes;
- 248 9. DQOL questionnaire score;
- 249 10. SF-36 questionnaire score;

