- 250 11. Number of daily injections;
- 251 12. Total daily dose of insulin;
- 252 13. Health care cost, total;
- 253 14. Health care cost, diabetes-related;
- 254 15. Total number of CBG checks/study;
- 255 16. Number of CBG checks/month;
- 256 17. Number of titration events by healthcare professional;
- 257 18. Number of titration events by patient;
- 258 19. Healthcare provider time during scheduled office (minutes/visit);
- 259 20. Healthcare provider time, unscheduled (total minutes);
- 260 21. Compliance with pharmacologic therapy;
- 261 22. Change in LDL cholesterol from baseline;
- 262 23. Change in Triglycerides from baseline;
- 263 24. Tolerability - defined as percentage of patients with side effects (other than  
264 hypoglycemia) related to the study medications;

265 25. Tolerability - defined by percentage of patients dropping out of the study due to  
266 side effects related to the study medications.  
267  
268

[figure not shown]
269 **RESEARCH DESIGN AND METHODS**

270 **Study type:**

- 271 • Single Center (UT Southwestern Medical Center at Dallas, TX)
- 272 • Randomized
- 273 • Single blind (evaluator)
- 274 • Two treatment arms (treatment and control)
- 275 • Length of intervention: 6 months
- 276 • Efficacy & safety trial
- 277 • Non-inferiority trial for primary outcome

278  
279 **Study Design:**

280 We will conduct a prospective, randomized, single blind, two-arm, parallel trial  
281 comparing two treatment regimens (liraglutide, detemir, and metformin versus aspart,  
282 detemir, and metformin) in patients with very uncontrolled (HbA1c>10%) type 2  
283 diabetes. The investigator performing the study related measurements will be blinded to  
284 the patients' treatment assignment.

285  
286  
287 Figure 1: Study design showing the run-in period, followed by the randomization visit  
288 and the 6-mo intervention period.  
289

290 The University of Texas Southwestern Medical Center Institutional Review Board will  
291 review the study and approve all relevant documents. Furthermore, study approval will be

292 obtained from Parkland Health and Hospital System (PHHS), which represents the study  
293 site.

294

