- 554 missed or if the participant voices concern.

555

556 **Other Assessments**

557 Treatment satisfaction and quality of life will be assessed at the randomization visit (Visit

558 2) and end of study (Visit 6) using a modified DQoL and SF-36 questionnaires. Total

559 score as well as individual domain scores will be analysed and reported.

560

561 Subject Compliance: Participants will bring all study medication to each appointment for

562 review and study drug will be distributed at each appointment (visit 1, 2, 3, 4, and 5).

563 Percent compliance will be calculated and recorded at each visit.

564

565 Healthcare Cost Assessment: At the conclusion of the study, the EPIC integrated medical  
566 record system will be queried for the data regarding all healthcare related expenditures.  
567 From this information a data subset of diabetes-related expenditure will also be reported.

568

569 Physician Time Assessment: Each physician interaction (office visit or phone visit) will  
570 be timed to compare the two treatment regimens with respect to burden on healthcare  
571 provider's time.

572

573

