### 735 **Statistical Analysis Plan**

736 All statistical analyses will be performed by the study statistician ([name]), who  
737 has extensive experience in clinical trials analysis.

738 Primary analysis: The primary analysis will be intention-to-treat (ITT) which will include  
739 all randomized participants who receive at least one dose of a study medication. The  
740 non-inferiority of liraglutide treatment strategy compared to standard basal-bolus insulin  
741 regimen will be assessed using a 95% confidence interval for the between treatment  
742 group net difference (month 6 minus month 0) in HbA1c at 6 months. This 95%  
743 confidence interval will be derived from the differences of least square means estimated  
744 from a mixed model repeated measures analysis. Non-inferiority of liraglutide treatment  
745 will be concluded if the upper limit of the 95% confidence interval is less than the non-  
746 inferiority margin of 0.4%.

747

748 Secondary analyses: We will also perform a per-protocol analysis comparing HbA1c  
749 response because, in non-inferiority hypothesis testing, the ITT analysis may be biased  
750 toward the null hypothesis. The per-protocol population is defined as the population who  
751 continued the assigned intervention as randomized for the duration of the study period.  
752 Secondary outcomes include the composite endpoint of HbA1c<7% with no  
753 hypoglycemia and no significant weight gain, a binary variable, which will be compared  
754 between the randomized study groups with a logistic regression model. The odds ratio  
755 and corresponding 95% confidence intervals will be reported. From healthcare related  
756 cost data, cost-effectiveness ratios will be summarized as point estimates with 95%  
757 confidence intervals, accounting for the skewness in the distribution of the ratio[50].  
758 Sensitivity cost analyses will be performed to further assess variables such as treatment  
759 failure and quality of life weights. Multiple logistic regression models will be constructed  
760 to evaluate any association of baseline covariates on treatment efficacy. Binary  
761 secondary endpoints will also be assessed with logistic regression models. Group  
762 comparisons and changes from baseline over time (study visits) of continuous secondary  
763 outcome variables will be analysed with mixed model repeated analysis. The logrank test  

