764 will be used to compare the pre-specified “treatment failure” end-point between groups.  
765 Safety endpoints and hypoglycemic and other adverse events will summarize in detail  
766 with descriptive statistics. The analysis of safety data will be performed for the ITT  
767 population.

768 Model assumptions regarding normality and covariance structure will be carefully  
769 assessed. Nonparametric tests or data transformations will be used if necessary to meet  
770 assumptions. Statistical analysis will be performed with SAS software (SAS Institute,  
771 Cary NC), particularly Proc Mixed for linear models with both fixed and random effects.

772 A two-sided alpha <5% will be considered significant for all analyses.

773

774 **Interim Analysis**

775 No interim analysis is planned.

776

777 **DATA HANDLING AND RECORD KEEPING:**

778 All data will be collected in strict compliance with the University's HIPPA rules.

779 Research records (source documents) will be kept in a double-locked filing system in a  
780 secure locked room. Collected data will be stored in an electronic study database will be  
781 encrypted and password protected and saved on the University's secure network. Only  
782 study personnel will have access to these records.

783

784 The institutional review board (IRB) governing this study may inspect the medical  
785 records of any patient involved in this study at any time.

786

787 Laboratory specimens will be collected under standard of care protocol at Parkland  
788 hospital laboratory and handled in accordance with the hospital policy.

789

790 The study blind will be maintained by the designated statistician and only broken by  
791 request from a treating physician in case of a medical emergency.

792

793 **ETHICS:**

794 Ethical Considerations:

795 1. Exclusion of non-English speakers- while translators are available during working  
796 hours, the investigators are worried that no translator will be available to assure  
797 safety measures at all times.

798 2. Compliance with Insulin Regimen- At times patients are not compliant with  
799 complicated insulin regimens and providers often continue to uptitrate insulin  
800 dosage when patients remain above HbA1c goal. If patient compliance improves  
801 once enrolled in the study, there is a higher risk of hypoglycemia. Every effort  
802 will be made at all visits to determine exactly what amount of insulin the patient  

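### The secondary outcomes are judged at a blanket two-sided 5% with no order, gate, adjustment or supportive label, and the composite can be declared superior even if HbA1c non-inferiority fails

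*Combined protocol and SAP*

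**What the plan says.** The closing rule of the Statistical Analysis Plan is "A two-sided alpha <5% will be considered significant for all analyses".

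The aim-and-hypothesis paragraph of Background and Significance proposes "that the two treatment regimens will have equal effectiveness, while the GLP-1 based", continuing "regimen will be superior with respect to all other variables". The next paragraph presents the study as evidence for future treatment guidelines.

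The Secondary outcomes list has 25 numbered items. Item 1 is the composite of HbA1c below 7%, no documented hypoglycemia and no significant weight gain, introduced with "The main secondary outcome is a less traditional but very patient-centric and". Item 25 begins "Tolerability - defined by percentage of patients dropping out of the study due to". Other Assessments adds the questionnaire domains: "score as well as individual domain scores will be analysed and reported".

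On methods, the Statistical Analysis Plan says of binary outcomes that "secondary endpoints will also be assessed with logistic regression models", and of continuous ones that "outcome variables will be analysed with mixed model repeated analysis". Treatment failure gets a logrank test. Safety endpoints, hypoglycemic events and adverse events are to be summarised descriptively.

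Sample Size Calculation powers the composite for superiority at two-sided 0.05 and powers no other secondary outcome. Neither section states an order of testing, a condition on the primary result, an adjustment, or that items 2 to 25 are exploratory.

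**The concern.** Many plans leave secondary outcomes unadjusted and do no harm, because nobody intends to claim anything from them. Here the plan states an affirmative rule for calling results significant, and superiority on the non-effectiveness variables is half of the trial's hypothesis. A reader who follows the text could report any secondary outcome with p below 0.05 as showing superiority, with no control over how many such findings chance produces.

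The missing gate is a separate problem and needs no count of tests. Weight and hypoglycemia are components of the composite, so the composite can favour liraglutide while the upper confidence limit for HbA1c lies above 0.4%. Nothing in the plan prevents a superiority claim on the composite in that case, although the trial's argument is comparable glycemic control first and advantages elsewhere second.

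**Working it through.** **The plan's own figures.** The documents give no family-wise error rate for the secondary outcomes, so there is none to reproduce. The primary power statement does reproduce: margin 0.4, SD 0.5, true difference 0, 44 per group and one-sided 0.025 give 0.960 by the noncentral t, as stated.

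**Counting the tests.**
- The list has 25 items. Without the composite, 24 remain.
- The hypothesis excludes effectiveness. On a natural reading that removes items 2 to 4 (HbA1c below 7%, glucose profile, treatment failure).
- The descriptive-statistics sentence covers hypoglycemia and adverse events, which removes items 7, 8, 24 and 25. Items 8, 24 and 25 are ambiguous, because they are binary and the plan also sends binary secondary endpoints to logistic regression.
- This leaves items 5, 6 and 9 to 23: 2 + 15 = 17.

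**Formula under independence, all nulls true.** At two-sided 5%, a result favouring liraglutide has probability 0.025 per test.
- At least one favouring liraglutide: 1 − 0.975^k. For k = 17 this is 0.350; for k = 24, 0.455.
- At least one in either direction: 1 − 0.95^k. For k = 17 this is 0.582; for k = 24, 0.708.

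**Under correlation.** The documents give no correlations, so a common value ρ is assumed and varied. With normal test statistics sharing one factor x, the chance of at least one result favouring liraglutide is 1 − ∫ Φ((1.96 − √ρ·x)/√(1−ρ))^k φ(x) dx. For either direction, Φ((−1.96 − √ρ·x)/√(1−ρ)) is subtracted inside the power.

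| ρ (assumed) | 17 tests, favouring liraglutide | 17 tests, either direction | 24 tests, favouring liraglutide | 24 tests, either direction |
|---|---|---|---|---|
| 0 | 35% | 58% | 46% | 71% |
| 0.3 | 25% | 49% | 31% | 60% |
| 0.5 | 19% | 39% | 23% | 46% |
| 0.7 | 14% | 27% | 16% | 31% |

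The lowest entries, 17 tests at ρ = 0.7, are 13.5% and 27.1% before rounding. Against nominal levels of 2.5% and 5% both are about 5.4 times too high.

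**What moves these figures.** Several outcomes overlap: total and diabetes-related cost, glucose checks per study and per month, weight change and weight loss above 5%. Independence is therefore an upper-end assumption for a given k. The number of daily injections differs by design, so a null there is unrealistic. In the other direction, domain scores, the two forms of weight change and comparisons over visits add tests beyond k.

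**The gate.** If HbA1c non-inferiority and the composite are tested side by side, the chance of a false claim for liraglutide on at least one of them is bounded by 0.025 + 0.025 = 0.05. In fixed sequence it is at most 0.025, and the composite keeps its full two-sided 5% level.

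**The case against.** The strongest reply is that this is ordinary practice. The primary analysis has one explicit rule that no secondary result can alter, and the composite already stands apart: it is named as the main secondary outcome, is the only one powered, and has its own model and effect measure. One sentence calling the rest supportive would then be enough. Most of this stands. The composite lacks a gate, not an identity, and the fix is close to that one sentence.

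Three stronger readings are tempting, and the documents do not support them.

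- A reader might infer that superiority is hypothesised and tested on all 24 other outcomes. The hypothesis excludes effectiveness, and hypoglycemia and adverse events are assigned to descriptive summaries. The sentence before the hypothesis names hypoglycemia, weight, quality of life, treatment burden, physician time and cost, so compliance and lipids (items 21 to 23) could be excluded too. That leaves 14 tests, and 1 − 0.975^14 = 30% favouring liraglutide if independent.
- A reader might infer that a false superiority claim for liraglutide is more likely than not. The 71% counts results in both directions. In the hypothesised direction the figure stays below one half even for 24 independent nulls; 28 would be needed to pass it.
- A reader might infer that one chance finding would prove the second half of the hypothesis. That half says superior on all other variables, which a single result cannot establish. The risk is of separate unprotected claims, outcome by outcome.

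**Conclusion.** The point holds in limited form. The plan declares significance at two-sided 5% for every analysis, makes superiority on the non-effectiveness variables part of its hypothesis, and provides no order, gate, adjustment or supportive label. For 17 null outcomes the chance of at least one false result favouring liraglutide is 19% to 35% for assumed correlations from 0.5 down to 0. For all 24 it is 23% to 46%. These figures rest on all the nulls being true, on an assumed common correlation, and on a count of tests that the plan itself leaves ambiguous. That the composite can be claimed after non-inferiority fails rests on none of these assumptions. The primary conclusion is not at risk. This is a worthwhile and inexpensive improvement to how the secondary results may be claimed.

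**What to change.** Replace the blanket significance sentence in the Statistical Analysis Plan with a two-step sequence:

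1. HbA1c non-inferiority, by the existing rule (upper 95% limit below 0.4%).
2. Only if that is shown, superiority on the composite at two-sided 5%.

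State that all other secondary outcomes and all questionnaire domain scores will be reported as estimates with unadjusted 95% confidence intervals, labelled supportive, with no confirmatory superiority claim. This also settles whether items 8, 24 and 25 are tested or only described. Reword the hypothesis in Background and Significance to match. A further test of HbA1c superiority is optional and not needed, since the protocol hypothesises equal effectiveness.

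The cost is wording only, with no added patients or data. The composite keeps its two-sided 5% level, but its claim now depends on the primary result. The downside is that the other secondary outcomes, including weight, quality of life and cost, can no longer support confirmatory claims.

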### 1008 **Collection, Recording and Reporting of Adverse Events**

1009 All events meeting the definition of an adverse event will be collected and reported from  
1010 the first trial related activity after the subject has signed the informed consent and until  
1011 the end of the study. This will be monitored by an independent committee (see below).  
1012 All serious and unexpected adverse events will be reported using FDA form 3500. All  
1013 reports of SAEs/SAR/SUSARs or any events reported to the local health authorities must  
1014 be sent to Novo Nordisk A/S within the same timeline used for reporting to regulatory  
1015 authorities (see below). Further information about safety related events will be provided  
1016 to Novo Nordisk A/S if specific requests are received.

1017

### 1018 **Data Safety Monitoring Board (DSMB)**

1019 An independent DSMB will be set up for the trial to oversee safety and perform ongoing  
1020 safety surveillance. The DSMB will be composed of 3 members who cover the relevant  
1021 specialty as well as an independent statistician:

- 1022 • [name] (Endocrinology)
- 1023 • [name] (Endocrinology)
- 1024 • [name] (Endocrinology)
- 1025 • [name] (Statistician)

1026 The first meeting will occur after the enrolment of 15 subjects or three months after the  
1027 first patient is enrolled, whichever comes first. The meetings will then occur on a  
1028 quarterly basis, although the board may request more frequent meetings as needed. A  
1029 formal report approved by all DSMB members will be sent to the PI and study  
1030 coordinator within 3 weeks of the meeting and then forwarded to the IRB.

1031

1032 All AEs will be presented at each meeting and will be available for informal review by  
1033 the DSMB at any time after study initiation. All SAE and unanticipated but related AE  
1034 will be promptly reported to the IRB (within 2 working days of PI's awareness for SAEs  
1035 and within 10 working days for other reportable AEs). We intend to comply with all  
1036 local legal, regulatory, and IRB requirements. We will also report to Novo Nordisk all  
1037 SAEs, SUSARs, and SADR at the same time such events are reported to regulatory  
1038 authorities or within 15 working days from the sponsor-investigator becoming aware of  
1039 such adverse events, whichever comes first.

1040

